4.0 Study Endpoints

4.1 Describe the primary and secondary study endpoints.

The primary endpoint of this study will be SpO2 measured at 3 standardized timepoints.

Secondary endpoints will include:

- SpO2 less than 90%
- End tidal CO2 measurement at 3 standardized timepoints
- Peak airway pressures measured at 3 standardized timepoints

• Occurrence of laryngospasm

4.2

The safety endpoint would be conversion to general endotracheal anesthesia.

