7.0 Inclusion and Exclusion Criteria*

- 7.1 Eligibility Criteria:
 - 1. Inclusion Criteria
 - 1. Patients undergoing laparoscopic inguinal hernia repair.
 - 2. Ages 12 months to 8 years of age

- American Society of Anesthesiologists Physical Status Classification ASA 1 or 2
 - 1. ASA 1- A normal, healthy patient
 - 2. ASA 2- A patient with mild systemic disease
- 4. Elective with appropriate NPO status
- 5. English speakers

2. Exclusion Criteria

- 1. Patients with current gastroesophageal reflux
- 2. Obesity (CDC >= 95^{th} %ile)
- 3. Contraindications to study protocol medications

7.2 Equitable Selection: Inclusion/exclusion criteria should be both fair and appropriate to the research question. If the study involves inclusion/exclusion criteria based on demographic characteristics such as sex, race/ethnicity, language, provide rationale for the criteria. For example, if excluding non-English speaking participants, provide rationale for why it is not possible to include non-English speaking participants.

Due to the limited sample size of patients enrolled, there is little to no anticipation of enrolling a non-English speaking patient. If a non-English speaking patient arises, the proper modifications will be put in place to present patient with translated consent forms and protocol, if need be.

7.3 Vulnerable Populations: Check any vulnerable populations that are being targeted for enrollment into the study: (Members of the following populations may not be included as participants in the research unless selected here.)

Children/Minors (under 7 years of age)

Children/Minors (7-17 years of age)

Neonates (infants less than 30 days old)

Reonates of Uncertain Viability (infants)

less than 30 days old)

Non-Viable Neonates (infants less than

30 days old)

□ Wards of the State

Fetuses

Pregnant Women

□ Adults with impaired decision-making capacity

CM Employees
 CM Students/Residents/ Fellows
 Economically or Educationally
 Disadvantaged Persons

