23.1 HIPAA Authorization

Select all applicable methods of HIPAA Authorization that apply to this study.

 \boxtimes Full Written HIPAA Authorization will be obtained (within the p/a/c form or standalone form)

⊠ Partial Waiver of HIPAA Authorization (e.g. waiver for recruitment and prescreening purposes only)

Must complete Addendum E: Waiver/Alteration of HIPAA Authorization

□ Alteration of HIPAA Authorization (some but not all required elements of an Authorization are present, e.g. signature will not be obtained) **Must complete** Addendum E: Waiver/Alteration of HIPAA Authorization

a) Describe which proposed elements to be altered.

□ Waiver of HIPAA Authorization (authorization will NOT be obtained)

☑ If Other, explain: We are requesting a Waiver of HIPAA Authorization at age 18 to allow data to continue to be retained in the DSDR without reconsenting former participants who have since turned 18. See Addendum E.

23.2 Specify the PHI for which accessing ("viewing") or recording ("writing down") is necessary for the purpose of this research:

To minimize risks, only the minimum necessary identifiable data should be accessed and/or recorded.

| 1. Name/Initials | □ Accessed only | ⊠ Recorded |
|---|----------------------|----------------------|
| All elements of date (except year) directly related to an individual (e.g. date of birth, admission date, discharge date, date of death) | □ Accessed only | ⊠ Recorded |
| 3. Medical record number | □ Accessed only | \boxtimes Recorded |
| 4. Account number | □ Accessed only | ⊠ Recorded |
| 5. Health plan identification number | □ Accessed only | □ Recorded |
| 6. Social Security Number | □ Accessed only | □ Recorded |
| 7. Device identifiers and serial number | □ Accessed only | □ Recorded |
| 8. Certificate/License number | □ Accessed only | □ Recorded |
| 9. Telephone number | \Box Accessed only | □ Recorded |
| 10. Fax number | □ Accessed only | □ Recorded |
| 11. Email addresses | □ Accessed only | □ Recorded |
| 12. Web addresses (URLs); Internet IP addresses | □ Accessed only | □ Recorded |
| 13. Street address, city, county, precinct, zip code or equivalent geographical codes | □ Accessed only | □ Recorded |
| 14. Full face photographic images and any comparable images | □ Accessed only | □ Recorded |
| 15. Biometric identifiers, including finger and voice print | □ Accessed only | □ Recorded |

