28.0 Statistical Analysis*

28.1 The data analysis will be a simple calculation of demographics and incidence of complications. Comparison between groups will be completed using chi square for categorical variables and t-test for continuous variables. Statistical significance will be set at p-value <0.05

We determined the targeted sample size of 50 patients using a power calculation using the following parameters: 90% power, 2.5% Type I error rate, non-inferiority limit of 5% point of SP02, no difference between treatments, and standard deviations of 1, 2, 5, and 10.

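### Section 28.1 plans an unadjusted t-test for the continuous endpoints; pre-specifying age as a covariate costs almost nothing and may gain precision if age predicts the outcome

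*Combined protocol and SAP*

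**What the plan says.** The comparative analysis is one sentence in section 28.1: "Comparison between groups will be completed using chi square for categorical variables and t-test for continuous variables". For the endpoints at issue here, the operative words are "t-test for continuous variables". Significance is set at p below 0.05. No covariate, regression or other model is named.

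Three endpoints in section 4.1 are continuous:
- the primary: "The primary endpoint of this study will be SpO2 measured at 3 standardized timepoints";
- a secondary: "End tidal CO2 measurement at 3 standardized timepoints";
- a secondary: "Peak airway pressures measured at 3 standardized timepoints".

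On age:
- Section 7.1 admits "Ages 12 months to 8 years of age".
- The table in section 23.2 marks as recorded the row that begins "All elements of date (except year) directly related to an individual", with date of birth as one of its examples.
- Section 28.1 also promises a "simple calculation of demographics and incidence of complications".
- Section 5.1 describes randomisation to the two airways and mentions no stratification or other balancing on age.

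Section 8.1 sets 25 children per arm. Section 28.1 gives the sizing inputs: 90% power, 2.5% Type I error, a limit of 5 SpO2 points, no true difference, and SDs of 1, 2, 5 and 10.

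**The concern.** The age range is wide and the arms are small. Neither the described randomisation nor the analysis deals with age. If age predicts an outcome, a t-test leaves that part of the variation in the standard error. The confidence interval set against the 5-point limit is then wider than it need be.

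There is also a practical risk. If the demographic table shows arms that differ in age, an adjustment added at that stage is post hoc and open to challenge. Age is fixed before randomisation, so a pre-specified adjustment is legitimate and needs no new data.

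**Working it through.** **Inputs from the documents.** Limit 5 points, true difference 0, n = 25 per arm, 90% power, Type I error 2.5%, SDs 1, 2, 5 and 10 (sections 8.1 and 28.1).

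**Assumptions, not in the documents.** Ages uniform over 1 to 8 years. Within-arm correlation r between age and outcome from 0 to 0.5.

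**1. The plan's own figure.** n per arm = 2[SD(z_α + z_0.90)/5]².
- SD 5, 2.5% one-sided: 2(1.960 + 1.282)² = 21.0, so 22 per arm and 44 in total (46 by the t distribution).
- SD 5, 2.5% split over two sides: 2(2.241 + 1.282)² = 24.8, so 25 per arm and 50 in total.

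So 50 is reproduced at SD 5 under the two-sided reading. At SDs 1, 2 and 10 the same formula gives 2, 8 and 170 (one-sided) or 2, 8 and 200 (two-sided). The figure is for an unadjusted comparison, and omitting age does not make it wrong.

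**2. Effect of adjustment on variance.** The adjusted variance is the unadjusted variance times (1 − r²), times about 1 + 1/46 for estimating one covariate with 50 children.

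| r | 1 − r² | with covariate cost |
|---|---|---|
| 0 | 1.00 | 1.022 |
| 0.1 | 0.99 | 1.012 |
| 0.3 | 0.91 | 0.930 |
| 0.5 | 0.75 | 0.766 |

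Break-even is where 1 − r² = 46/47, so r = √(1/47) = 0.146. At r = 0.5 the reduction is 25% before the covariate cost and 23% after it.

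**3. Effect on power at SD 5, one-sided 2.5%.** Unadjusted SE = 5√(2/25) = 1.414, noncentrality 5/1.414 = 3.536, 48 df, power 93.4%. With age in the model there are 47 df, and the noncentrality is 3.536 divided by the square root of the last column above:
- r = 0: 3.498, power 92.9%;
- r = 0.3: 3.667, power 94.9%;
- r = 0.5: 4.039, power 97.7%.

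Reading 2.5% as two-sided lowers the levels but keeps the pattern: by noncentral t, 88.5% unadjusted, 87.7% at r = 0 and 95.4% at r = 0.5. At SDs 1 and 2, power is about 100% either way.

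**4. Chance imbalance in age.** SD of age = 7/√12 = 2.02 years. SE of the difference in mean age = 2.02√(2/25) = 0.57 years. P(difference of at least 1 year) = 2[1 − Φ(1/0.57)] = 8%.

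The shift in the SpO2 contrast per year of imbalance is r × SD/2.02. At SD 5:
- r = 0.3: 0.3 × 5/2.02 = 0.74 points;
- r = 0.5: 0.5 × 5/2.02 = 1.24 points.

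That is 15% to 25% of the 5-point limit.

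**The case against.** The strongest reply is that the plan contains no error here. Under randomisation the unadjusted difference is unbiased, the t-test keeps its Type I error, and its standard error already allows for chance imbalance. About 92% of allocations would differ by less than a year in mean age. Below r of about 0.15, adjusting costs precision. At SDs 1 and 2 it changes nothing, and at SD 5 unadjusted power at one-sided 2.5% is already above 90%. All of this stands.

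It is also true that section 23.2 is a standard form row with date of birth as one example, and that section 28.1 does not name age among the demographics. But eligibility depends on age, so it has to be known for every child.

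A reader might infer more than the documents support:
- **That precision is being lost.** This needs an age-outcome correlation. The documents give none for SpO2, EtCO2 or airway pressure, and the gain may differ between them.
- **That age adjustment secures power if the SD is 10.** It does not. Power goes from 41% to 43% at r = 0.3 and 51% at r = 0.5. The sample-size basis at that SD is a separate matter.
- **That SpO2 before induction should also be a covariate.** The documents do not show that it is collected.

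The reply does not remove the asymmetry: about half a point of power at risk if age is irrelevant, against several points if it is moderately predictive.

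**Conclusion.** The point holds as a low-severity improvement. The analysis is unadjusted, age should be available and spans a wide range, and no balancing on age is stated. Over r = 0 to 0.5, adjustment moves the variance from about 2% higher to 23-25% lower. Power at SD 5 and one-sided 2.5% moves from 93.4% to between 92.9% and 97.7%. The shift of 0.7 to 1.2 SpO2 points applies only to an allocation that differs by one year in mean age, at SD 5 and r = 0.3 to 0.5. The 8% chance of at least such a difference rests on the uniform age distribution. The size for EtCO2 and airway pressure in their own units cannot be worked out, because the documents give no SD for either.

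A model also supplies something that section 28.1 lacks. A t-test at p below 0.05 asks whether the arms differ, whereas section 2.2 states a non-inferiority hypothesis. An arm coefficient with its confidence interval can be set directly against the 5-point limit.

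**What to change.** In section 28.1:
- For SpO2, EtCO2 and peak airway pressure, at each of the three timepoints, replace the t-test with a linear model containing arm and age in years as a continuous term.
- Conclude non-inferiority on SpO2 from the two-sided 95% confidence interval for the arm coefficient (LMA minus ETT): the lower limit must lie above −5 points. This matches a one-sided 2.5% error rate. Do not conclude it from a p-value above or below 0.05 for a difference.
- Report the unadjusted difference and its confidence interval as supportive.
- Name age explicitly among the data to be collected, so that the covariate is not left to inference.

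How the three timepoints combine into one primary conclusion still has to be stated; this change does not settle it.

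The cost is a few lines of text, one degree of freedom per model, and about half a point of power at SD 5 if age is unrelated to the outcome. Sample size and trial conduct do not change.

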8.0 Local Number of Participants

8.1 Indicate the total number of participants or charts to be enrolled locally as well as the accrual goal. If the study includes multiple groups or cohorts, be sure to describe the number of participants required for each cohort. If one of the groups includes a chart review, each chart is considered a participant and needs to be reflected in the numbers below.

□ Prisoners

| | Group 1 | Group 2 | Totals |
|--|---------|-----------------|--------|
| | | (if applicable) | |
| Enrollment Goal: Number of participants to be enrolled = the number of participants to be consented or to be screened for chart reviews. | 25* | 25* | 50* |

*The total enrollment goal will remain 50 patients, but an additional 20 patients will be enrolled to accommodate screening failures and withdrawals.

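### Section 28.1 does not say which SD or which sidedness produced N = 50, and the 90% power stated there is not met at SD 10, one of its own listed values

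*Combined protocol and SAP*

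**What the plan says.** Section 28.1 contains the whole sample size justification, in one sentence. It opens "We determined the targeted sample size of 50 patients using a power calculation using the following parameters: 90% power", continues "2.5% Type I error rate, non-inferiority limit of 5% point of SP02", and ends "no difference between treatments, and standard deviations of 1, 2, 5, and 10". Section 8.1 sets 25 per group and says "The total enrollment goal will remain 50 patients", with 20 further patients to cover screening failures and withdrawals.

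The sentence reports no sample size or power for the individual SDs, names none of the four as the design value, and does not give the sidedness of the 2.5%. Elsewhere in section 28.1 the group comparisons are described as chi-square and t-tests, with "Statistical significance will be set at p-value <0.05". Section 3.2 (preliminary data) gives no SpO2 variability. Sections 1.0 and 4.1 define the primary endpoint as SpO2 at three timepoints and do not say how the three readings are combined.

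**The concern.** For a fixed margin, the required sample size grows with the square of the SD. Between SD 1 and SD 10 it changes about a hundredfold, so a single N cannot correspond to 90% power at all four values. Read as written, the sentence attaches 90% to each of them.

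The hypothesis in section 2.2 is non-inferiority. A reader uses the planned power to judge how likely the trial is to settle that question, and how to interpret a failure to show it. The 90% figure holds only up to a certain SD. That limit is not stated, and one of the plan's own SDs lies well beyond it.

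**Working it through.** **Inputs.** From section 28.1: margin 5 percentage points, true difference 0, power 90%, error rate 2.5%, SD 1, 2, 5 or 10, t-test. From section 8.1: n = 25 per arm. Two assumptions are needed. The SD is taken as that of the single analysed SpO2 value, because the plan does not say how the three timepoints are combined. Both sidedness readings are run: α = 0.025 (one-sided) and α = 0.0125 per side (two-sided 2.5%).

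**Step 1: try to reproduce 50.** Normal formula per arm: n = 2(z₁₋α + z₀.₉₀)² SD² / 5².
- One-sided 2.5%, SD 5: 2(1.960 + 1.282)² × 25/25 = 21.01, so 22 per arm, 44 in total. The t-based total is 46.
- Two-sided 2.5%, SD 5: 2(2.241 + 1.282)² × 25/25 = 24.82, so 25 per arm, 50 in total. The t-based total is 54.
- One-sided 2.5%, SD 10: 84.06, so 85 per arm, 170 in total. The t-based total is 172.
- Two-sided 2.5%, SD 10: 99.29, so 100 per arm, 200 in total. The t-based total is 202.

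At SD 1 and 2 the t-based totals are 6 and 10 (one-sided) or 6 and 12 (two-sided). The only combination tried that returns 50 is two-sided 2.5%, SD 5, normal approximation.

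**Step 2: power of 25 per arm.** Noncentral t with df = 48 and ncp = 5 / (SD × √(2/25)). The ncp is 17.68, 8.84, 3.54 and 1.77 at SD 1, 2, 5 and 10. The critical t is 2.011 (one-sided 2.5%) or 2.314 (two-sided 2.5%).

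| SD | One-sided 2.5% | Two-sided 2.5% |
|---|---|---|
| 1 | >99.9% | >99.9% |
| 2 | >99.9% | >99.9% |
| 5 | 93.4% | 88.5% |
| 10 | 41.0% | 30.2% |
| Largest SD with 90% power | 5.34 | 4.89 |

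By normal approximation, SD 5 gives 94.2% (one-sided) or 90.2% (two-sided), SD 10 gives 42.4% or 31.8%, and the limits are 5.45 and 5.02. The method matters only for whether SD 5 reaches 90% on the two-sided reading.

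**Step 3: can another reading rescue SD 10?**
- 5% per side, 25 per arm: 53.9%.
- All 70 enrolled patients analysed (35 per arm), one-sided 2.5%: 54.1%. The 90% limit moves to SD 6.36.
- SD 10 per reading, mean of three readings, one-sided 2.5%, 25 per arm: the analysed SD is 10 × √((1 + 2ρ)/3), and power is about 85%, 56% and 46% at correlations of 0, 0.5 and 0.8.

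**Step 4: what SD 10 would mean for the result.** The 95% confidence interval half-width is 2.011 × 10 × √(2/25) = 5.69 points, wider than the 5-point margin. With no true difference, the interval would typically cross the margin.

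**The case against.** The strongest reply is that the list is a grid of scenarios. One calculation cannot use four SDs at once, and the sentence does not say outright that 50 gives 90% at each of them. This is probably how the list arose, and the exact match at two-sided 2.5% and SD 5 is the best clue that SD 5 was the design case. The clue is not proof: it depends on the normal approximation, while the planned t-test needs 54. The grid reading also leaves the gap in place, because a grid without its results and without the chosen row does not tell the reader where 90% applies.

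It can also be said that the 41% depends on treating the SD as that of one analysed value. That is right, and the figure is conditional on it. Averaging three readings raises power at SD 10, but with 50 patients at one-sided 2.5% it stays below 90% even if the readings are independent. Only stacked assumptions get there: independent readings (analysed SD 10/√3 = 5.77) together with all 70 patients analysed (limit 6.36). The plan states neither, and the claim is made for 50.

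The p<0.05 threshold might be taken to settle the matter in favour of one-sided 2.5%. It follows the general sentence on chi-square and t-tests and is not tied to the non-inferiority test, so both readings are kept.

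A reader might go further and infer that the trial is underpowered, or that a non-inferiority claim from it would be unsafe. The documents support neither. They give no SpO2 SD from data and do not mark SD 10 as the working case. A non-inferiority conclusion rests on the observed confidence interval against the margin, not on planned power. If the SD were near 10, the likely result is an inconclusive trial, not a false claim.

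**Conclusion.** The point holds as a defect in how the power calculation is stated. The SD and the sidedness behind 50 are missing, and the 90% figure fails at SD 10: 41.0% at one-sided 2.5% and 30.2% at two-sided 2.5%. SD 1 and 2 are amply covered. SD 5 is covered on the one-sided reading (93.4%) and is borderline on the two-sided reading (88.5% by t, 90.2% by normal approximation). The limit for 90% power is an SD of about 5.3 or 4.9 respectively. These figures assume 25 evaluable patients per arm, equal SDs, no true difference and one analysed SpO2 value per patient. Whether 50 is enough in practice depends on an SD that the documents do not give.

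**What to change.** Restate the power sentence in section 28.1 so that 90% is not claimed for all four SDs. It should:

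- name the SD and the sidedness actually used to reach 50, which the sponsor must confirm from its own calculation, since neither can be recovered from the text;
- say which SpO2 value that SD describes;
- give the power of 50 patients (25 per arm) at SD 1, 2, 5 and 10 on that basis;
- give the largest SD for which 90% holds: about 5.3 if one-sided 2.5%, about 4.9 if two-sided 2.5%.

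The figures for either choice are in the table under the working. If the original calculation cannot be found, the sentence should report power by SD for a declared sidedness, without naming a design SD after the fact.

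The cost is the restated sentence. Sample size, enrolment and conduct do not change. The downside is that the plan will openly show low power at SD 10.

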29.0 Data and Specimen Management*

29.1 Data Management: Describe how data will be handled, including:

Data will be collected by reviewing the participant's medical record after the circumcision procedure is complete. Data will be recorded in REDCap, securely stored on the CMH servers, and only accessible to IRB-approved study team members. Data will be rolled into the Department of Surgery Data Repository (DSDR, IRB#18020079) at the time of data collection, and will remain stored in the DSDR under the approved provisions of the repository for potential use in future research studies.

29.2 Specimen Management: *Describe how specimens will be handled, including:*

1. N/A

29.3 Biosafety Information

Will this study involve handling, transporting, or shipping any potentially hazardous biological material at/from a Children's Mercy location (e.g., blood, stool, saliva, tissue)?

🗆 Yes

 \boxtimes No

Will this study involve processing any potentially hazardous biological material at a Children's Mercy location (e.g., blood, stool, saliva, tissue)?

🗆 Yes

🛛 No

If processing potentially hazardous biological materials, where will this work be conducted?

□ Pediatric Clinical Research Unit (PCRU)

□ Children's Mercy Research Institute Biorepository (CRIB)

□ Children's Mercy Research Institute labs (mySafety ID#:)

□ Other location

If "Other location," identify the location and mySafety ID# of the corresponding IBC protocol:

Location: _____

mySafety ID#: _____

30.0 Storing of Data and/or Banking of Specimens for Future Research

30.1 If this study involves storing of data or banking of leftover specimens for future research, indicate how the use will be managed:

Contributing data and/or leftover specimens to an existing CM repository protocol (myIRB#18020079, Department of Surgery Data Repository (DSDR))

□ Contributing data and/or leftover specimens to an existing non-CM repository (Institution/Repository Name: ______

□ Not contributing to an existing repository for the management of data/specimens for future research use.

□ Other:

31.0 Provisions to Monitor the Data to Ensure the Safety of Participants

This section is required when research involves more than Minimal Risk to participants.

31.1 In addition to the Principal Investigator, which individual or group will be responsible for monitoring the data and safety for this study?

Sponsor or Sponsor Designee (including the Sponsor CRO)
 Data and Safety Monitoring Board (DSMB) or Data Safety Monitoring Committee (DSMC)

Independent Monitor (s)

□ Internal Committee at CM

Other: ____N/A_____

31.2 Data Safety Monitoring Plan: If a DSMB charter or other external monitoring plan is available, upload in the myIRB application, Other Attachments section. If such a charter/plan is not available, describe:

1. There are no plans for a DSMB for this study.

STUDY MANAGEMENT

